7 SAFETY MONITORING

This section defines the types of adverse events that should be reported and outlines the procedures for appropriately collecting, grading, recording, and reporting them.

7.1 Definitions for Recording of Safety Events

All safety events observed under this protocol are reported through the electronic data capture system for the duration of the study. Some safety events arising under certain defined conditions are recorded on specific forms as follows.

- Any allergic symptoms observed during in-clinic dosing will be recorded directly on the Escalation / In-Clinic Dosing form (also referred to as a Study Product Administration form), and are not recorded on an adverse event form (to avoid duplicate reporting) unless the event is considered a serious adverse event. These symptoms are, however, by definition, adverse events (Section 7.2) and will be reported as such in the database.
- Safety events related to accidental food exposure are recorded on an Accidental Food Exposure form. They are not to be reported on an adverse event form (to avoid duplicate reporting) unless the event is considered a serious adverse event, as defined below (Section 7.3 and Section 7.4.2).
- For any event occurring after a subject has signed the informed consent form that meets the definition of anaphylaxis, an Anaphylaxis Episode form will be completed and forwarded to the CRO's Reporting Center within 24 hours of its occurrence and/or the site's being notified of the event (Section 7.7.2), if the event is associated with any of the following:
 - An emergency room visit;

- Hospitalization;
- More than 2 doses of epinephrine being given as treatment for the same episode;
- Assessment of the anaphylaxis as severe, as defined in Appendix 3.
- If any safety event meets the definition of a serious adverse event (whether or not related to dosing), it will also be recorded on an adverse event (AE)/serious adverse event (SAE) form.
- Skin prick test reactions are not considered adverse events unless the reaction, or a complication from the procedure, is considered a serious adverse event, as defined below (Section 7.4.2).
- Food challenge reactions that occur in the clinic are captured on study specific forms and are not reported on an adverse event form (to avoid duplicate reporting) unless the event is considered a serious adverse event, as defined below (Section 7.4.2).
 - As study product is not used in the DBPCFCs, no AEs occurring from Screening DBPCFC can be treatment-related (referring to treatment with study product).
 - For food challenge reactions that occur at the Exit DBPCFC, it will also usually be the case that study product was not the cause of the reaction, as study product is not used in the challenge. There is, however the possibility that dosing with study product in the days prior to Exit DBPCFC could contribute to a reaction encountered during the challenge. The investigator must determine if dosing with study product in the days prior to Exit DBPCFC likely contributed to any observed reaction. If so, the investigator should indicate the level of the relatedness, and provide a brief explanation as to the manner in which prior dosing with study product was thought to be contributory.
- All serious adverse events are reported on the AE/SAE form set in addition to the Skin Prick form or an Oral Food Challenge form if the event occurred during 1 of these procedures. All other safety events that occur throughout the study are reported on the AE/SAE form set.

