3.7.3 Secondary Safety Endpoints, North America and Europe

- The safety of peanut OIT based on adverse events (AEs) including serious adverse events (SAEs) in the following 5 age groups: 4 to 17 years, 4 to 11 years, 12 to 17 years, 18 to 55 years, and 4 to 55 years, inclusive
- Use of epinephrine as a rescue medication during OIT (Initial Escalation, Up-dosing, and Maintenance Periods) in the following 5 age groups: 4 to 17 years, 4 to 11 years, 12 to 17 years, 18 to 55 years, and 4 to 55 years, inclusive
- Frequency of anaphylaxis during OIT (Initial Escalation, Up-dosing, and Maintenance Periods) in in the following 5 age groups: 4 to 17 years, 4 to 11 years, 12 to 17 years, 18 to 55 years, and 4 to 55 years, inclusive
- Frequency of allergic reaction (hypersensitivity) AEs occurring during the Up-dosing versus the Maintenance Period, normalized for duration of treatment in the following 5 age groups: 4 to 17 years, 4 to 11 years, 12 to 17 years, 18 to 55 years, and 4 to 55 years, inclusive
- Frequency of accidental ingestions of peanut and other allergenic foods in the following 5 age groups: 4 to 17 years, 4 to 11 years, 12 to 17 years, 18 to 55 years, and 4 to 55 years, inclusive
- Severity of adverse events associated with accidental ingestions of peanut and other allergenic foods in the following 5 age groups: 4 to 17 years, 4 to 11 years, 12 to 17 years, 18 to 55 years, and 4 to 55 years, inclusive
- Frequency of premature discontinuation of dosing due to AEs; and frequency of premature discontinuation of dosing due to chronic/recurrent gastrointestinal (GI) AEs in the following 5 age groups: 4 to 17 years, 4 to 11 years, 12 to 17 years, 18 to 55 years, and 4 to 55 years, inclusive

• Assessment of asthma control using the Asthma Control Test questionnaire in subjects with asthma in the following 5 age groups: 4 to 17 years, 4 to 11 years, 12 to 17 years, 18 to 55 years, and 4 to 55 years, inclusive

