- (North America sites only) Optional collection of saliva sample for exploratory biomarker development (Appendix 6)
- Monitoring for adverse events (AEs), including allergic symptoms (Section 6.7)

- Subjects will be instructed to continue to follow a peanut-avoidant diet for the duration of the study.
- Subjects and parents or guardians will additionally receive teaching about food/peanut allergy according to the investigational site's established standards. This is to include at a minimum the following topics (some or all of which may be addressed in a comprehensive anaphylaxis action plan):
 - Recognition of an allergic reaction and of the symptoms of anaphylaxis
 - When and how to administer epinephrine via auto-injector
 - Requirement to go to nearest emergency facility following use of epinephrine autoinjector
 - Ways to minimize the risk of accidental exposure to peanut in, and outside of, the home (may be supplemented by referral to recognized food allergy organizations for access to additional learning materials)

All screening procedures must be completed no later than 28 days from the signing of the informed consent/assent form. The Initial Escalation Day-1 visit should occur within 10 days of the Screening DBPCFC.

The laboratory values and clinical findings, including those from the Screening DBPCFC, will serve as the baseline measures for comparison to subsequent measures obtained during the course of the study.

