7.8.3 Notifying the Data Safety Monitoring Committee

The Reporting Center will provide the DSMC with listings of all SAEs on an ongoing basis. Furthermore, the DSMC will be informed of expedited reports of SAEs. Periodic reports from the DSMC as to the overall safety of the ongoing study, and recommendations regarding continuation will be sent to the investigators for forwarding to their IRBs/ECs if requested.

Investigational sites are instructed to report episodes of anaphylaxis within 24 hours of their occurrence and/or the sites being notified of the event to the Reporting Center for forwarding to the DMSC if the event is associated with any of the following:

- An emergency room visit;
- Hospitalization;
- More than 2 doses of epinephrine being given as treatment for the same episode;
- Assessment of the anaphylaxis as severe, as defined in Appendix 3.

An initial Anaphylaxis Episode form containing the information known to the site at this time will be transmitted to the Reporting Center. The Reporting Center will then relay to the sponsor and DSMC the individual anaphylaxis reports as they are obtained. The investigational site will supplement the initial Anaphylaxis Episode report with additional information pertaining to an event as it becomes available and will forward the information to the Reporting Center.

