## **10.3. ADVERSE EVENTS**

Symptoms that are collected during in-clinic dosing visits (including DBPCFC) are not captured on the adverse event CRF page, unless the symptom is determined to be an SAE or the subject experienced an anaphylaxis episode. Thus, each of the summaries of adverse events described below will be presented in 2 different ways:

- 1. Including only events collected on the adverse event CRF page, excluding in-clinic dosing symptoms other than SAEs and anaphylaxis episodes.
- 2. Combining adverse events collected on the adverse event CRF page and dosing symptoms collected at the in-clinic dosing visits.

All reported adverse events (AEs) will be classified into System Organ Class (SOC) and Preferred Term (PT) using Medical Dictionary for Regulatory Activities (MedDRA) version 18.1.

Treatment-emergent adverse events (TEAEs) are defined as those AEs with onset after the first dose of study drug. AEs with onset prior to first dose of study drug will be included in subject listings, but not summarized. TEAEs will be summarized for the safety population by age group (4-17 years, 4-11 years, 12-17 years, 18-55 years, and 4-55 years) and by study period as follows:

- Initial Escalation: All events beginning after the first dose of study drug on Day 1 and prior to the first at-home Up-dosing administration.
- Up-dosing: All events beginning after the first dose at-home Up-dosing administration and prior to the first at-home dose of 300 mg (which starts the Maintenance Period).
- Maintenance: All events beginning after the first dose at-home dose of 300 mg, including events after the Exit DBPCFC but prior to the rollover to ARC004.
- Overall: Across initial escalation, up-dosing, and maintenance periods.

Summaries that are displayed by system organ class and preferred terms will be ordered by descending incidence of system organ class and preferred term within each system organ class. Summaries displayed by preferred term only will be ordered by descending incidence of preferred term. Summaries of the following types will be presented:

• Overall summary of number of unique TEAEs and treatment-emergent serious adverse events (TESAEs), subject incidence of TEAEs and TESAEs meeting various criteria, and exposure adjusted incidence rates of TEAEs and TESAEs

meeting various criteria, where exposure incidence rates are defined as the total number of events divided by the total number of subject-years at risk during the study period;

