#### **10.15. ANAPHYLAXIS EPISODES**

All reported anaphylactic reaction episodes will be listed by age group, treatment group, and subject.

Each anaphylaxis reaction will be identified by the following triggers:

- DBPCFC
- Study drug

- Food allergen other than study drug while on treatment
- Non-food allergen while on treatment
- Other

Anaphylaxis reactions will be summarized in the Safety population separately for the following study periods:

- Screening DBPCFC, Peanut Challenge
- Screening DBPCFC, Placebo Challenge
- Overall Treatment Period (including Initial Escalation, Up-dosing, Maintenance)
- Initial Escalation
- Up-dosing
- Maintenance
- Exit DBPCFC, Peanut Challenge
- Exit DBPCFC, Placebo Challenge

For study periods of overall treatment period, Initial Escalation, Up-dosing, and Maintenance, additional summaries will be included by trigger (any trigger, study drug, food allergen other than study drug while on treatment, and non-food allergen while on treatment)

The number of anaphylactic reactions, the number and percent of subjects experiencing an anaphylactic reaction, the number and percent of subjects experiencing an anaphylactic reaction by maximum severity using the Murano Grading Scale (Muraro, et. Al), the number of subjects experiencing an anaphylactic reaction that was an SAE, the number of subjects experiencing an anaphylactic reaction that required use of epinephrine, and the number of subjects experiencing an anaphylactic reaction that involved individual symptoms will be summarized for each study period and trigger combination.

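### Protocol 7.1 and SAP 10.3 disagree on how in-clinic anaphylaxis is recorded, so non-severe clinic episodes can drop out of the anaphylaxis endpoint

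*Protocol*

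**What the plan says.** - **Endpoint.** Protocol 3.7.3 lists "Frequency of anaphylaxis during OIT (Initial Escalation, Up-dosing, and Maintenance Periods" among the secondary safety endpoints, in five age groups. It sets no threshold for severity, treatment or setting.
- **Anaphylaxis Episode form.** Under Protocol 7.1, "an Anaphylaxis Episode form will be completed and forwarded to the CRO's Reporting Center within 24 hours of its occurrence" or of the site learning of it, "if the event is associated with any of the following": an emergency room visit, hospitalization, more than 2 epinephrine doses for the episode, or a severe grade under Appendix 3.
- **In-clinic symptoms, protocol.** Protocol 7.1 sends allergic symptoms seen at in-clinic dosing to the dosing form. They "are not recorded on an adverse event form (to avoid duplicate reporting) unless the event is considered a serious adverse event". The section adds that they are still adverse events and enter the database as such.
- **In-clinic symptoms, SAP.** SAP 10.3 says in-clinic symptoms are not on the adverse event page "unless the symptom is determined to be an SAE or the subject experienced an anaphylaxis episode". That second exception is absent from Protocol 7.1.
- **Expedited reporting.** Protocol 7.8.3 repeats the four triggers: "Investigational sites are instructed to report episodes of anaphylaxis within 24 hours of their occurrence", for onward transmission to the DSMC.
- **Analysis.** SAP 10.15: "All reported anaphylactic reaction episodes will be listed by age group, treatment group, and subject". It tabulates episodes by period, cause, maximum severity, seriousness and epinephrine use, but does not say which form supplies them.

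**The concern.** The endpoint counts anaphylaxis of any severity, while the only stated rule for completing the dedicated form selects on severity and on the care received. The adverse event form would be the fallback, but Protocol 7.1 closes it to non-serious reactions in clinic. The SAP is written as if it were open.

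This matters because the first dose at each new level is given in clinic (Protocol 5.2), so reactions to dose increases tend to arise in the setting where the recording rules conflict. Both arms follow the same rules, but any loss falls where the reactions are. In ARC001, treatment-emergent hypersensitivity events occurred in 90% of AR101 and 50% of placebo subjects (Protocol 1.2.2.1). An incomplete count would therefore mainly understate anaphylaxis on AR101, and more in Up-dosing than in Maintenance.

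**Working it through.** The plan gives no figure to reproduce, so the check is a comparison of text.

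**1. Which episodes have no trigger?** Those that are mild or moderate, treated with 0 to 2 epinephrine doses, and involve no emergency room visit or hospitalization. Appendix 5 makes most of these non-serious: one or two intramuscular injections are ordinarily not intensive therapy, and calling a mild or moderate episode without intensive therapy an important medical event needs a detailed rationale.

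**2. Where does each episode go?**

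| Episode | Anaphylaxis Episode form (7.1) | AE form under Protocol 7.1 | AE page under SAP 10.3 |
|---|---|---|---|
| Severe, any setting | Required | Home: yes. Clinic: only if serious | Yes |
| Non-severe, home, epinephrine used | Required if the emergency visit takes place | Yes | Yes |
| Non-severe, home, no epinephrine or emergency visit | Not required | Yes | Yes |
| Non-severe, non-serious, clinic, 0 to 2 epinephrine doses | Not required | **No** | **Yes** |

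The second row follows because subjects are taught the "Requirement to go to nearest emergency facility following use of epinephrine" auto-injector (Protocol 6.2), and Protocol 6.7.6 says the same of epinephrine given outside the clinic. The home entries on the AE form follow from the closing rule of 7.1, which sends all other safety events there; reactions to accidental food exposure are an exception, with their own form. The last row is the contradiction.

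**3. What remains for the last row?** SAP 10.6 describes the in-clinic record as severity of pre-specified symptoms, presence of dose-related symptoms, and whether the dose was tolerated. No anaphylaxis diagnosis or stage is mentioned. The symptoms survive; the classification that SAP 10.15 needs may not.

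**4. Direction of any effect.** Let S be severe episodes, M non-severe episodes, and x the share of M not recorded as anaphylaxis. The count falls from S + M to S + M(1 − x). The severe share rises from S/(S + M) to S/(S + M(1 − x)), because severe grade is itself a trigger.

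**5. Size.** Missed share = c × u × m, where c is the share of all episodes that occur in clinic, u the share of those that are untriggered and non-serious, and m the share of those that no source records as anaphylaxis. The documents give none of the three. If sites work as SAP 10.3 describes, m = 0 and nothing is lost. If they follow 7.1 literally and no other source is used, m = 1 and the loss is c × u. Purely as an assumption, c of 30% to 70% and u of 50% to 95% put that ceiling between 0.3 × 0.5 = 0.15 and 0.7 × 0.95 = 0.665. The floor is zero in every case.

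**The case against.** The strongest reply is that the four triggers are expedited-reporting criteria and not a case definition. Protocol 7.8.3 uses them for a 24-hour report destined for the DSMC, and Appendix 5 speaks of DSMC reporting criteria. Protocol 7.4.3.1 makes anaphylaxis an event of special interest and requires the basis of every diagnosis to be documented, with no trigger. Protocol 7.2 requires timing, treatment and relatedness of dosing reactions to be recorded, and Protocol 7.5.2 has an Adjudication Committee review selected events, naming anaphylaxis. SAP 10.3 reads as a description of what is captured and was written after enrollment closed. The separate rows in SAP 10.15 for serious episodes and for those needing epinephrine presuppose episodes that are neither. SAP 10.16 adds a search for systemic reactions that investigators did not call anaphylaxis.

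Much of this stands. Expedited reporting is probably what the triggers were meant for, the symptom data are kept, and nothing shows that an episode was lost. But Protocol 7.1 does not confine the triggers to forwarding, and no section says which form applies to an untriggered episode. Protocol 7.4.3.1 names no case report form. The committee can review only reports that reach it. The SAP cannot create adverse event entries that the protocol tells sites not to make. SAP 10.16 is a separate table that is not added to SAP 10.15, and it does not say whether it searches in-clinic dosing symptoms.

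**Conclusion.** The contradiction between Protocol 7.1 and SAP 10.3 is real and bears on a secondary safety endpoint. A non-serious, mild or moderate in-clinic episode without a trigger may be held only as dosing symptoms. The anaphylaxis frequency in SAP 10.15 can then be too low and its severity mix tilted towards severe, to a different degree for clinic and home reactions. This rests on sites reading 7.1 literally and on SAP 10.15 drawing on the Anaphylaxis Episode form and the adverse event page; the SAP does not name its source.

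A reader might infer that the endpoint is undercounted, perhaps by 15% to 66%. The documents do not support that. The range is a product of assumed shares, and it treats every untriggered episode as missed, which is the open question. The size cannot be derived. The point deserves correction before database lock, but it does not demonstrate bias.

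**What to change.** 1. **Protocol 7.1 and SAP 10.3:** use one rule. Every investigator-diagnosed anaphylaxis episode, whatever its severity or setting, is recorded as anaphylaxis on the Anaphylaxis Episode form and the adverse event page. The four triggers govern only 24-hour forwarding to the Reporting Center and DSMC. Link the entry to its dosing symptoms so that the combined summary in SAP 10.3 does not count one reaction twice.
2. **SAP 10.15:** name the source form or forms and count every such episode.
3. **Visits already done:** add to the blinded pre-lock review in SAP 11 a check for in-clinic dosing reactions that meet the Appendix 3 criteria but have no anaphylaxis record, and query the site. The investigator decides. A programmed Appendix 3 rule should not replace that diagnosis in the main count: Appendix 3 gives criteria for a suspected diagnosis, and applying it to clinic data alone would create a new difference between settings.
4. **SAP 10.16:** state that the search runs on adverse event page and in-clinic dosing-symptom data combined.

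The cost is a wording change, a note to sites, a round of queries and some programming on data already collected. Reported anaphylaxis incidence may rise.

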7.2 Dosing Symptoms as Adverse Events

Although signs and symptoms of allergic reaction, especially those that are mild in severity, are frequent and expected occurrences in response to dose escalation during OIT, they still constitute AEs. As such, the start and stop times of dose-related allergic reactions, as well as any therapeutic interventions, and relatedness to study product will need to be recorded (Section 7.7.1).

It is common for allergic reactions, especially allergic reactions to food allergens, to manifest with multiple symptoms. Investigator sites will record each individual symptom as an AE and indicate the symptom is part of an allergic reaction by checking the "allergic reaction" box on the AE form.

7.3 Accidental Food Exposures

In order to report the occurrence of a safety event associated with accidental food ingestion, subjects will be instructed to contact the site study coordinator or investigator for any adverse event. The subject may be asked to return to the site. These events will be reported as follows:

- Accidental Food Exposure form will be completed for each of these events in addition to events where consumption of peanut without a reaction occurs.
- If the accidental food ingestion safety event meets the definition of a serious adverse event, as defined below (Section 7.4.2), the AE/SAE form will be completed as well.

7.4 **Definitions**

7.4.1 Adverse Event (AE) or Medical Event

An **adverse event** is any untoward medical occurrence in humans, whether or not considered drug related which occurs during the conduct of a clinical trial. Any change in clinical status, ECGs, routine labs, x-rays, physical examinations, etc., that is considered clinically significant by the study investigator is considered an AE.

Suspected adverse reaction is any adverse event for which there is a reasonable possibility that the drug caused the adverse event. A reasonable possibility implies that there is evidence that the drug caused the event.

Adverse reaction is any adverse event caused by the drug.

7.4.2 Serious Events (Serious Adverse Events, Serious Suspected Adverse Reactions or Serious Adverse Reactions)

A serious adverse event including a serious suspected adverse reaction or serious adverse reaction as determined by the investigator or the sponsor is any event that results in any of the following outcomes:

- 1. Death
- 2. Life-threatening AE (Life-threatening means that the study subject was, in the opinion of the investigator or sponsor, at immediate risk of death from the reaction as it occurred.)
- 3. Inpatient hospitalization or prolongation of existing hospitalization
- 4. Persistent or significant incapacity or substantial disruption of the ability to conduct normal life functions
- 5. Congenital abnormality or birth defect
- 6. Important medical event that may not result in 1 of the above outcomes, but may jeopardize the health of the study subject or require medical or surgical intervention to prevent 1 of the outcomes listed in the above definition of serious event.

It is anticipated that the most likely cause of SAEs in this study will be anaphylaxis; however, not all occurrences of anaphylaxis are necessarily SAEs. Guidance for determining when anaphylaxis should be reported as an SAE is provided in **Appendix 5**.

